9.2.4. Procedures for Immune-Mediated Dermatitis

Monitor subjects for signs and symptoms of dermatitis such as rash and pruritus. Unless an alternate etiology has been identified, signs or symptoms of dermatitis should be considered immune mediated. Recommendations for management of dermatitis are shown in Table 5.

Table 5. Recommended Approach to Handling Dermatitis.

	Withhold/ Discontinue Pembrolizumab and Epacadostat	Guidance for Restarting Study Treatment	Supportive Care
Grade 1	No action.	N/A.	For mild to moderate dermatitis, such as localized rash and pruritus, treat symptomatically. Administer topical or systemic corticosteroids if there is no improvement of symptoms within 1 week.
Grade 2	No action	N/A.	For mild to moderate dermatitis, such as localized rash and pruritus, treat symptomatically. Administer topical or systemic corticosteroids if there is no improvement

Version Date: 11/09/2017

			of symptoms within 1 week.
Grade 3 and 4	Withhold epacadostat and pembrolizumab in subjects with moderate to severe signs and symptoms of rash. Permanently discontinue epacadostat and pembrolizumab in subjects with Stevens-Johnson syndrome, toxic epidermal necrosis, or rash complicated by full thickness dermal ulceration or by necrotic, bullous, or hemorrhagic manifestations.	If AE resolves to ≤ Grade 1 or baseline within 4 weeks, subject may restart at the same dose and schedule for both pembrolizumab and epacadostat. If rash is mild and Grade 3 only based on BSA, and resolves without oral steroids, treatment may be restarted at the previous dose. For an AE that does not resolve to ≤ Grade 1 or baseline within 4 weeks, epacadostat should be reduced as per Table 1, but pembrolizumab may be restarted at the same dose and schedule. If AE does not resolve within 6 weeks, study treatment with both study drugs should be discontinued.	Administer systemic corticosteroids at a dose of 1 to 2 mg/kg per day of prednisone or equivalent. When dermatitis is controlled, corticosteroid tapering should occur over a period of at least 1 month.

9.2.5. Procedures for Immune-Mediated Neuropathies

Subjects should be monitored for symptoms of motor or sensory neuropathy such as unilateral or bilateral weakness, sensory alterations, or parenthesis. Recommendations for management of neuropathies are shown in Table 6.

Table 6. Recommended Approach to Handling Neuropathies.

	Withhold/ Discontinue Pembrolizumab and Epacadostat	Guidance for Restarting Study Treatment	Supportive Care
Grade 1	No action.	N/A.	Provide symptomatic treatment.
Grade 2	May withhold pembrolizumab and epacadostat.	May return to treatment if improves to Grade 1 or baseline. If AE resolves within 4 weeks, subject may restart at the same dose and schedule for both pembrolizumab and epacadostat. For an AE that does not resolve ≤ Grade 1 or baseline within 4	Consider systemic corticosteroids in addition to appropriate symptomatic treatment.

		weeks, epacadostat should be reduced as per Table 1, but pembrolizumab may be restarted at the same dose and schedule. If AE does not resolve within 6 weeks, study treatment with both study drugs should be discontinued.	
Grade 3 and 4	Discontinue pembrolizumab and epacadostat.	Not applicable. Any exceptions require PI approval.	Consider initiation of systemic corticosteroids at a dose of 1 to 2 mg/kg per day prednisone or equivalent for severe neuropathies. Institute medical intervention as appropriate for management of severe neuropathy.

9.2.6. Procedures for Immune-Mediated Endocrinopathies

Subjects should be monitored for clinical signs and symptoms of hypophysitis, adrenal insufficiency (including adrenal crisis), and hyper- or hypothyroidism. Subjects may present with fatigue, headache, mental status changes, abdominal pain, unusual bowel habits, and hypotension or with nonspecific symptoms which may resemble other causes such as brain metastasis or underlying disease. Unless an alternate etiology has been identified, signs or symptoms of endocrinopathies should be considered immune-mediated.

Thyroid function tests and clinical chemistries should be monitored at the start of treatment, before each dose, and as clinically indicated based on symptoms. In a limited number of subjects, hypophysitis was diagnosed by imaging studies through enlargement of the pituitary gland. Recommendations for management of endocrinopathies are shown in Table 7.

Table 7. Recommended Approach to Handling Endocrinopathies.

	Withhold/ Discontinue Pembrolizumab and Epacadostat	Guidance for Restarting Study Treatment	Supportive Care
Grade 1	No action.	N/A.	Provide symptomatic treatment.
Grade 2	May withhold pembrolizumab and epacadostat.	May return to treatment if improves to Grade 1 or baseline. If AE resolves within 4 weeks ≤ Grade 1 or baseline, subject may restart at the same dose and	Initiate systemic corticosteroids treatment at a dose of 1 to 2 mg/kg per day of prednisone or equivalent, and initiate

Version Date: 11/09/2017

		schedule for both pembrolizumab and epacadostat. For an AE that does not resolve ≤ Grade 1 or baseline within 4 weeks, epacadostat should be reduced as per Table 1, but pembrolizumab may be restarted at the same dose and schedule. If AE does not resolve within 6 weeks, study treatment with both study drugs should be discontinued.	appropriate hormone replacement therapy.
Grade 3	Withhold or discontinue pembrolizumab and epacadostat.	May return to treatment if improves to Grade 1 or baseline. If AE resolves ≤ Grade 1 or baseline within 4 weeks, subject may restart at the same dose and schedule for both pembrolizumab and epacadostat. For an AE that does not resolve ≤ Grade 1 or baseline within 4 weeks, epacadostat should be reduced as per Table 1, but pembrolizumab may be restarted at the same dose and schedule. If AE does not resolve within 6 weeks, study treatment with both study drugs should be discontinued.	Consider initiating systemic corticosteroids treatment at a dose of 1 to 2 mg/kg per day of prednisone or equivalent, and initiate appropriate hormone replacement therapy.
Grade 4	Discontinue both pembrolizumab and epacadostat.	Not applicable. Any exceptions require PI approval.	Consider initiation of systemic corticosteroids at a dose of 1 to 2 mg/kg per day of prednisone or equivalent, and initiate appropriate hormone replacement therapy.

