- Subjects must agree to pre- and on-treatment tumor biopsies. Use of outside archived tumor tissue for a baseline biopsy is not permitted. An optional research biopsy at the time of progression will also be discussed with these patients, however, is not mandatory. Subjects in whom biopsy is technically not feasible or in whom would result in unacceptable risk, in the opinion of the investigator, may be exempted from the biopsy requirement with approval by the principal investigator.

Key Exclusion Criteria:

• Treatment with chemotherapy (not including Tyrosine Kinase Inhibitors) or radiotherapy within 4 weeks (6 weeks from nitrosoureas or mitomycin C), or treatment with monoclonal antibody therapy within 4 weeks prior to start of study treatment.

Note: No minimum washout period is required for tyrosine kinase inhibitor therapy (eg, imatinib or sunitinib).

- Patients must have recovered from adverse events (greater than grade 1) due to prior anticancer therapy, except for stable chronic toxicities such as alopecia.
- Participation in any other clinical study with investigational drug received within 28 days or 5 half lives (whichever is longer) before first dose.
- Subjects who have received prior anti-PD-1 or anti-PD-L1 antibody therapy, or an IDO inhibitor. Subjects who have received experimental vaccines or other immune therapies should be discussed with the principal investigator to confirm eligibility.
- Subjects receiving immunosuppressive treatment, including chronic steroids (at a dose equivalent to > 10 mg/day of prednisone) within 14 days prior to first study treatment. Inhaled or topical steroids or systemic steroids (at dose ≤10 mg/day of prednisone) is permitted.

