6.2. Exclusion Criteria

1. Treatment with chemotherapy (not including Tyrosine Kinase Inhibitors) or radiotherapy within 4 weeks (6 weeks from nitrosoureas or mitomycin C), or treatment with monoclonal antibody therapy within 4 weeks prior to start of study treatment.

Note: No minimum washout period is required for tyrosine kinase inhibitor therapy (eg, imatinib or sunitinib).

- 2. Patients must have recovered from adverse events (greater than grade 1) due to prior anticancer therapy, except for stable chronic toxicities such as alopecia.
- 3. Participation in any other clinical study with investigational drug received within 28 days or 5 half lives (whichever is longer) before first dose.
- 4. Subjects who have received prior anti-PD-1 or anti-PD-L1 antibody, or an IDO inhibitor. Subjects who have received experimental vaccines or other immune therapies should be discussed with the principal investigator to confirm eligibility.
- 5. Any prior ≥ Grade 3 immune-related adverse event (irAE) while receiving immunotherapy, or any unresolved irAE > grade 1.
- 6. Subjects receiving immunologically based treatment for any reason, including chronic steroids or prednisone (at dose >10 mg/day of prednisone) within 14 day prior to first study treatment. Inhaled or topical steroids or systemic steroids (at dose ≤10 mg/day of prednisone) is permitted.

Version Date: 11/09/2017

- 7. Subjects with any active or inactive autoimmune process (eg, rheumatoid arthritis, moderate or severe psoriasis, multiple sclerosis, inflammatory bowel disease) or who are receiving systemic therapy for an autoimmune disease. Exceptions include vitiligo, hypothyroidism controlled on hormone replacement, type I diabetes, Grave's disease, adrenal insufficiency on stable replacement doses of steroids (prednisone ≤10 mg/day or equivalent), or with principal investigator approval.
- 8. No prior organ allograft or allogenic bone marrow transplantation.
- 9. History of (noninfectious) pneumonitis that require steroids or current pneumonitis.
- 10. A diagnosis of another active malignancy with the following exceptions: basal or squamous cell carcinoma of the skin, in-situ carcinoma of the cervix, isolated elevation of prostate-specific antigen, indolent secondary malignancies not requiring active therapy, or with the approval of the principal investigator. Subjects with a completely treated prior malignancy and no evidence of disease for ≥ 2 years are eligible.

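### Table 7 directs high-dose steroids for a Grade 2 endocrinopathy but makes the same dose optional at Grades 3 and 4

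*Combined protocol and SAP*

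**What the plan says.** Section 9.2.6 covers hypophysitis, adrenal insufficiency, and hyper- and hypothyroidism, and refers all of them to Table 7. The steroid wording in its Supportive Care column is:

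- Grade 2: "Initiate systemic corticosteroids treatment at a dose of 1 to 2 mg/kg per day of prednisone or equivalent"
- Grade 3: "Consider initiating systemic corticosteroids treatment at a dose of 1 to 2 mg/kg per day of prednisone or equivalent"
- Grade 4: "Consider initiation of systemic corticosteroids at a dose of 1 to 2 mg/kg per day of prednisone or equivalent"

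Hormone replacement does not soften in the same way. It is to be started at Grade 2, and the Grade 3 and Grade 4 cells each continue with "and initiate appropriate hormone replacement therapy". Grade 1 asks for symptomatic treatment only.

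**The concern.** The dose stays constant while the instruction goes from an order to an option as the event becomes more severe. Read literally, a patient with a Grade 2 endocrinopathy is sent to high-dose prednisone more firmly than a patient with a Grade 4 one. At Grade 2 the study drugs only may be withheld, so the steroid could be given while immunotherapy continues.

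What is at stake is how patients at two sites are managed. If the Grade 2 verb is the slip, some milder events are directed to a steroid dose that the authors did not intend. If the Grade 3 and 4 verbs are the slip, severe events get weaker guidance than intended. The documents do not say which.

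**Working it through.** The plan gives no figure to reproduce on this point. The check is a side-by-side reading, with a short calculation for scale.

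**1. Within Table 7.**

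| Grade | Study drugs | Steroid, 1 to 2 mg/kg/day | Hormone replacement |
|---|---|---|---|
| 2 | may be withheld | initiate | initiate |
| 3 | withhold or discontinue | consider | initiate |
| 4 | discontinue both | consider | initiate |

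Drug action escalates with grade and hormone replacement stays directive. Only the steroid instruction weakens. The Grade 2 cell crosses a page break, but its continuation concerns hormone replacement alone, so the pattern does not come from how the text was extracted.

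**2. Across the six tables in Section 9.2.**

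| Table | Steroid at Grade 2 | Steroid at Grades 3 and 4 | Change with grade |
|---|---|---|---|
| 2, pneumonitis | indicated, no dose | indicated, no dose | same |
| 3, enterocolitis | 0.5 to 1 mg/kg if symptoms last over a week | directive, 1 to 2 mg/kg | firmer |
| 4, hepatitis | 0.5 mg/kg if elevation lasts over a week | directive, 1 to 2 mg/kg | firmer |
| 5, dermatitis | topical or systemic if no improvement in a week | "Administer systemic corticosteroids at a dose of 1 to 2 mg/kg per day of prednisone or equivalent" | firmer |
| 6, neuropathies | "Consider systemic corticosteroids in addition to appropriate symptomatic treatment" | consider, 1 to 2 mg/kg | same verb |
| 7, endocrinopathies | initiate, 1 to 2 mg/kg | consider, 1 to 2 mg/kg | weaker |

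One table of six weakens.

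**3. Where 1 to 2 mg/kg appears in Section 9.2.** Tables 3, 4, 5 and 6 at Grades 3 and 4 give four places; Table 7 at Grades 2, 3 and 4 gives three; Section 9.2.7, for severe reactions, gives one. The total is 4 + 3 + 1 = 8. Only one of the eight, Table 7 Grade 2, lies below Grade 3 or a severe reaction.

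**4. Scope.** Section 9.2.6 names the thyroid conditions beside the pituitary and adrenal ones. Table 7 has no thyroid row or exception, and the Grade 2 steroid instruction carries no condition. Thyroid events are therefore covered by scope, though the cell does not name them.

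**5. Scale.** The inputs are the pembrolizumab counts among 2,799 subjects in Section 11.1.7: hypothyroidism 237, hyperthyroidism 96, adrenal insufficiency 22, hypophysitis 17. Maximum accrual is 23 (Section 5.2).

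- Hypothyroidism: 237/2799 = 8.5%; 23 × 237/2799 = 1.9 expected cases.
- All four types, if no patient has two: 237 + 96 + 22 + 17 = 372; 372/2799 = 13.3%; 23 × 372/2799 = 3.1 expected patients.

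These are any-grade rates for pembrolizumab alone. The Grade 2 share and the rates with epacadostat added are not given.

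**The case against.** The strongest reply is that Table 7 is headed as a recommended approach and reads as a menu for a whole class of events. Taken literally, the same rows would also give hormone replacement to a hyperthyroid patient, which suggests that the clinician is meant to select what applies. Replacement therapy stays directive at every grade from 2 to 4, and drug action does escalate. Section 8.3.2 permits immune suppressants for immune toxicity, so no prohibited-medication rule is broken.

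All of that stands, and it limits the consequence. It does not explain why the steroid verb is firm only at the lower grade. Section 9.2.7 does not settle the matter either: it addresses other reactions, and its directive wording for severe events points the opposite way from Table 7 at Grades 3 and 4.

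A reader might go further and infer that the protocol itself shows steroids to be wrong for thyroid events, because exclusion criterion 7 in Section 6.2 excepts "hypothyroidism controlled on hormone replacement". The documents do not support that. The exception concerns pre-existing disease at entry and is not a treatment rule for a new immune-mediated event on study.

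A reader might also compare the dose with the 10 mg/day prednisone limit in the synopsis exclusion criteria. That is an eligibility limit for chronic steroids, and the comparison would apply equally to every 1 to 2 mg/kg instruction in Section 9.2, so it does not measure this inconsistency.

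**Conclusion.** The inconsistency is real and rests on the text alone. Table 7 is the one table of six that inverts, and its Grade 2 cell is the one place of eight where the full dose is set below Grade 3 or a severe reaction. It is worth correcting as a safety-management point. It does not touch the two-stage design, the response endpoint or their analysis.

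The expected counts show only that endocrine events are likely enough for the table to be used. They assume that the pembrolizumab-alone rates apply here. A reader might take 8.5% as a ceiling on how often the Grade 2 cell would apply, but it bounds only Grade 2 hypothyroidism at that rate, because three other named conditions share the row. Nor do the documents show which verb is the slip: the directive wording for severe events in Tables 3 to 5 and Section 9.2.7 points one way, and Table 6 the other.

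**What to change.** Edit the Supportive Care cells of Table 7 so that the steroid instruction at Grades 3 and 4 is at least as strong as at Grade 2.

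- **Smallest edit:** change the Grade 2 verb from *initiate* to *consider*. This matches Table 6, fits the optional withholding of study drug at Grade 2, and removes the unconditional high-dose steroid for thyroid events.
- **If the clinical team wants directive steroids** for conditions such as hypophysitis or adrenal crisis: name those conditions and make the verb *initiate* for them at Grades 3 and 4.
- **Leave in place** the existing option to consider steroids for Grade 3 and 4 thyroid events. The inconsistency does not require its removal, and nothing in the documents supports it.

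The cost is a text amendment to one table. The investigator's statement on the signature page requires IRB approval before a change is implemented, and Section 21.2 requires the affiliate site's IRB to approve amendments within 90 days of distribution. No new assessments are needed.

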9.2.7. Procedures for Other Immune-Mediated Adverse Reactions, Including Ocular Manifestations

Epacadostat and pembrolizumab should be permanently discontinued for severe immune-mediated adverse reactions. Systemic corticosteroids treatment should be initiated at a dose of 1 to 2 mg/kg per day of prednisone or equivalent for severe immune-mediated adverse reactions.

Corticosteroid eye drops should be administered to subjects who develop uveitis, iritis, or episcleritis. Epacadostat and pembrolizumab should be permanently discontinued for immune-

Version Date: 11/09/2017

mediated ocular disease that is unresponsive to local immunosuppressive therapy.

9.3. Procedures for Subjects Exhibiting Serotonin Syndrome

There is a theoretical chance that epacadostat could cause an increase in serotonin levels in the brain that might trigger serotonin syndrome (SS) when administered in combination with other serotonergic agents. This syndrome has been most closely associated with use of MAOIs, Demerol®, linezolid, or methylene blue; all of these agents are prohibited during the study. Serotonin reuptake inhibitors (SSRIs) and serotonin/norepinephrine reuptake inhibitors (SNRIs) are permitted in the study. The following procedures will be implemented if subjects exhibit the signs/symptoms of SS, including tremor, hyperreflexia, spontaneous, ocular, or inducible clonus, together with agitation, fever, diaphoresis, or muscle rigidity:

- Immediately interrupt epacadostat administration. *Administration of pembrolizumab may continue*.
- Immediately interrupt any SSRI or SNRI administration.
- Provide appropriate medical management of the subject until all signs/symptoms are resolved (eg, IV fluids and/or sympathomimetic amines for hypotension, benzodiazepines for agitation, administration of 5-hydroxytryptamine antagonists such as cyproheptadine).
- If subject chooses to remain in the study, restart treatment with epacadostat after the SSRI or SNRI has been discontinued, no sooner than 5 half-lives have elapsed for the specific SSRI or SNRI in question and after resolution of signs/symptoms of SS. The SSRI or SNRI treatment MAY NOT be restarted.
- If subject chooses to withdraw from the study, or must restart treatment with SSRI or SNRI, the subject should be scheduled for a follow-up visit. Treatment with SSRI or SNRI may be initiated 2 weeks after resolution of signs and symptoms of SS.

10. ADVERSE EVENTS: LIST AND REPORTING REQUIREMENTS

10.1. Adverse events

See sections 11.1.7 and 11.2.7 for a list of adverse events related to pembrolizumab and epacadostat, respectively.

10.2. Definitions

Adverse Event:

An adverse event (AE) is any untoward or unfavorable medical occurrence in a human subject, including abnormal sign, symptom or disease, temporally associated with the subject's participation in research, Please note: laboratory, vital signs or ECG abnormalities are to be recorded as Adverse Events only if they are medically relevant (clinically significant): symptomatic, requiring corrective treatment, leading to treatment discontinuation and/or fulfilling a seriousness criterion.

Version Date: 11/09/2017

Therefore, abnormal results of diagnostic procedures are considered to be adverse events if the abnormality:

- results in study withdrawal
- is associated with a serious adverse event
- is associated with clinical signs or symptoms
- leads to additional treatment or to further diagnostic tests
- is considered by the investigator to be of clinical significance

Serious Adverse Event:

Adverse events are classified as serious or non-serious. A serious adverse event is any AE that is:

- fatal
- life-threatening
- requires inpatient hospitalization/prolongation of existing hospitalation, unless:
 - o routine treatment or monitoring of the studied indication, not associated with any deterioration in condition (procedures such as central line placements, paracentesis, pain control)
 - o elective or pre-planned treatment for a pre-existing condition that is unrelated to the indication under study and has not worsened since the start of study drug
 - o treatment on an emergency outpatient basis for an event not fulfilling any of the definitions of an SAE given above/below and not resulting in hospital administrations
 - o social reasons and respite care in the absence of any deterioration in the patient's general condition
- results in persistent or significant disability or incapacity
- a congenital anomaly or birth defect
- an important medical event

Important medical events are those that may not be immediately life threatening, but are clearly of major clinical significance. They may jeopardize the subject, and may require intervention to prevent one of the other serious outcomes noted above. For example, drug overdose or abuse, a seizure that did not result in in-patient hospitalization or intensive treatment of bronchospasm in an emergency department would typically be considered serious.

All adverse events that do not meet any of the criteria for serious events should be regarded as non-serious adverse events.

Unanticipated Problem:

An unanticipated problem is any incident, experience or outcome involving risks to subjects or others in any human subjects research that meets all of the following criteria:

• Unexpected (in terms of nature, severity or frequency) given (a) the research procedures that are described in the IRB-approval protocol and informed consent document, and (b) the characteristics of the subject population being studied;

Version Date: 11/09/2017

- Related or possibly related to participation in such research (e.g., there is a reasonable possibility that the incident, experience or outcome may have been caused by the procedures involved in such research); and
- Suggests that the research places subjects or others at a greater risk of harm (including physical, psychological, economic or social harm) than was previously known or recognized.

Adverse Event Reporting Period

The study period during which adverse events must be reported is normally defined as the period from the initiation of any study procedures (e.g., after the first dose of study treatment) to the end of the study treatment (e.g., last dose of study treatment) and/or follow-up. For this study, the study treatment follow-up is defined as 90 days following the last administration of study treatment, or 90 days following the decision to remove the subject from study treatment, whichever is earliest.

Baseline/Preexisting Condition

A baseline/preexisting condition is one that is present at the start of the study. A preexisting condition should be recorded as an adverse event if the frequency, intensity, or if the character of the condition worsens during the study period.

General Physical Examination Findings

At screening, any clinically significant abnormality should be recorded as a preexisting condition. At the end of the study, any new clinically significant findings/abnormalities that meet the definition of an adverse event must also be recorded and documented as an adverse event.

Post-study Adverse Event

All unresolved adverse events should be followed by the investigator until the events are resolved, the subject is lost to follow-up, or the adverse event is otherwise explained. At the last scheduled visit, the investigator should instruct each subject to report any subsequent event(s) that the subject, or the subject's personal physician, believes might reasonably be related to participation in this study.

Abnormal Laboratory Values

A clinical laboratory abnormality should be documented as an adverse event if any one of the following conditions is met:

- The laboratory abnormality is not otherwise refuted by a repeat test to confirm the abnormality
- The abnormality suggests a disease and/or organ toxicity
- The abnormality is of a degree that requires active management (e.g., change of dose, discontinuation of the drug, more frequent follow-up assessments, further diagnostic investigation, etc.).

Hospitalization, Prolonged Hospitalization or Surgery

Any adverse event that results in hospitalization or prolonged hospitalization should be documented and reported as a serious adverse event unless specifically instructed otherwise in this protocol. Any condition responsible for surgery should be documented as an adverse event if the condition meets the criteria for an adverse event.

Neither the condition, hospitalization, prolonged hospitalization, nor surgery are reported as an adverse event in the following circumstances:

Version Date: 11/09/2017

- Hospitalization or prolonged hospitalization for diagnostic or elective surgical procedures for a preexisting condition. Surgery should **not** be reported as an outcome of an adverse event if the purpose of the surgery was elective or diagnostic and the outcome was uneventful.
- Hospitalization or prolonged hospitalization required to allow efficacy measurement for the study.
- Hospitalization or prolonged hospitalization for therapy of the target disease of the study, unless it is a worsening or increase in frequency of hospital admissions as judged by the clinical investigator.

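### Section 10.2 contradicts itself on one kind of admission: a diagnostic or elective surgical stay for a pre-existing condition that has worsened on study drug

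*Combined protocol and SAP*

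**What the plan says.** Three paragraphs of section 10.2 (Definitions) deal with pre-existing conditions.

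- **Serious Adverse Event.** An AE is serious if it "requires inpatient hospitalization/prolongation of existing hospitalation, unless" one of the listed exceptions applies. The exception relevant here covers elective or pre-planned treatment of a "pre-existing condition that is unrelated to the indication under study and has not worsened since the start of study drug".
- **Baseline/Preexisting Condition.** "A preexisting condition should be recorded as an adverse event if the frequency, intensity, or if the character of the condition worsens".
- **Hospitalization, Prolonged Hospitalization or Surgery.** An AE that leads to admission "should be documented and reported as a serious adverse event unless specifically instructed otherwise in this protocol". The next sentence says that the condition behind an operation counts as an AE when it satisfies the AE definition. A list of exemptions follows, opening with "Neither the condition, hospitalization, prolonged hospitalization, nor surgery are reported as an adverse event in the following circumstances". Its first bullet is "Hospitalization or prolonged hospitalization for diagnostic or elective surgical procedures for a preexisting condition". Its third bullet, on therapy for the target disease, withdraws the exemption if there is worsening or more frequent admission. The first bullet has no such limit.

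**The concern.** The first bullet of the exemption list omits the condition on which the SAE definition depends: that the pre-existing condition has not worsened since study drug began. It also exempts the condition itself, not just the admission. A site that follows the bullet literally would leave out an event that two earlier paragraphs of the same section require it to report.

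Safety and tolerability is a secondary objective (section 2.2). SAE classification triggers the 24-hour report to the data and safety monitoring committee (10.4.3), the 24-hour report to one manufacturer (10.4.4) and the report within two working days to the other (10.4.5). There are two sites, and each could rely on a different paragraph. The exemption list is the more permissive text, so any resulting error is towards under-reporting.

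**Working it through.** The plan gives no figure to reproduce, and the point involves no error rate, power or sample size. The check applies each rule in section 10.2 to the possible cases.

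| Case | SAE definition | Baseline-condition paragraph | First bullet of the exemption list | Result |
|---|---|---|---|---|
| (a) Not worsened, unrelated to GIST, elective surgical admission | Exempt, not an SAE | Not an AE | Not reported | Agree |
| (b) Not worsened, diagnostic admission | The exception is worded for treatment, but there is no AE to be made serious | Not an AE | Not reported | Agree in effect |
| (c) Worsened on study drug, diagnostic or elective surgical admission | Exception unavailable, so an SAE | AE | Neither condition nor admission reported | **Conflict** |
| (d) Worsened on study drug, admission neither diagnostic nor elective surgical (acute, unplanned) | SAE | AE | Does not apply | Agree: SAE |

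Cases (a) and (b) show that the lists may differ in wording without harm while the condition is stable, because a stable pre-existing condition is not an AE. Case (d) shows that the bullet's scope ends at diagnostic and elective surgical procedures. Only case (c) fails, and worsening is the qualifier that separates it from (a) and (b).

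Can case (c) be resolved from the text?

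1. The general rule in the hospitalisation paragraph gives way to specific instructions elsewhere in the protocol. The bullet is such an instruction, so a site could treat it as controlling.
2. The sentence on conditions leading to surgery points the other way, since a worsened condition does satisfy the AE definition. But the list that follows begins by excluding the condition, so the paragraph contradicts itself. That sentence also covers surgery only and does not help with a diagnostic admission.
3. The third bullet of the same list has a worsening carve-out and the first does not. A reader could conclude that worsening is immaterial under the first.

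No reading settles the matter without setting one of the paragraphs aside.

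On scale, maximum accrual is 23, so one patient is 1/23 = 4.3 percentage points of a crude SAE rate. This is a unit of measurement, not an estimate, because the documents do not say how often case (c) would arise.

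**The case against.** The strongest reply is that the rest of the protocol already captures these events. Section 10.3 requires every AE in the study period to be recorded. Section 12.2.6 requires all AEs, serious or not, to be recorded whatever their cause. The baseline-condition paragraph and the sentence just before the exemption list agree. On this view, one loosely drafted bullet stands against several clear rules, and a sensible site would report the event. This reply stands in part: the bullet is the outlier, and the protocol's overall intent is to record worsening. It does not remove the defect, because the bullet is written as an exception to those general rules.

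Four stronger readings are tempting, and the documents do not support them.

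- **That any admission for a worsened condition escapes reporting.** It does not; see case (d).
- **That flares of permitted autoimmune or endocrine conditions would be lost.** Section 6.2 does admit such patients ("Exceptions include vitiligo, hypothyroidism controlled on hormone replacement, type I diabetes", among others). But nothing in the documents suggests that a flare would typically lead to elective surgery or a purely diagnostic stay, and admission to treat one falls outside the bullet. Section 9.2.6 also presumes endocrinopathies to be immune-mediated unless another cause is found, and requires thyroid tests and chemistries before each dose.
- **That the SAE rate would be materially distorted.** There is no frequency to support this. Section 17 specifies no SAE-rate analysis, and section 15.10 sets no numerical toxicity boundary that a small shift could cross.
- **That the diagnostic exemption should go, or that the bullet must also require the condition to be unrelated to GIST.** Neither is needed to remove the contradiction. Mandatory biopsies make some planned diagnostic admissions foreseeable.

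**Conclusion.** The inconsistency is real and limited to one case. For a diagnostic or elective surgical admission for a pre-existing condition that has worsened since the start of study drug, the SAE definition and the baseline-condition paragraph together give an SAE, while the first bullet of the exemption list, read literally, gives no report of the condition or the admission. The bullet also conflicts with the sentence immediately before its own list.

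The conclusion rests on the literal text and on the possibility that a site treats the bullet as a controlling exception. Affected events are probably uncommon, and their number cannot be estimated from the documents. The consequence is confined to safety reporting; the response-rate endpoint, the two-stage rule and the efficacy analyses do not depend on it. The edit is still worth making, because a stated rule followed as written would drop reportable events from a secondary objective and from expedited reporting.

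**What to change.** Reconcile the three paragraphs of section 10.2 as follows.

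1. Add to the first bullet of the hospitalisation exemption list the qualifier that the pre-existing condition has not worsened since the start of study drug.
2. State in the same place that the baseline-condition paragraph governs, so that a worsened condition is recorded as an AE and any admission for it is assessed for seriousness under the SAE definition.

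The cost is a wording amendment, matching changes to any SAE form instructions that repeat the list, and possibly a few more SAE reports. Planned diagnostic or elective admissions for stable conditions stay exempt.
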